Additionally, the retro-perspective study conducted by McDonald et al identified and analyzed twenty patients who were prescribed Ivabradine (2.5mg once daily) specifically for POTS; this provided valuable insight for utilizing Ivabradine as a treatment option for POTS. McDonald et al concluded that 55% of patients who continued to take Ivabradine reported a decrease in palpitations and tachycardia episodes and 44% of those patients reported a decrease in fatigue. These improvements in fatigue symptoms are consistent with the findings of Ewan et al. However, 20% of these patients were also taking floninef or midodrine in conjunction with Ivabradine, which may have confounded the true efficacy of Ivabradine. Nonetheless, they were able to show that Ivabradine was well-tolerated in patients with POTS and the adverse side effects were minimal.

Similarly, Sutton et al prescribed Ivabradine (5mg twice daily) to twenty POTS patients and concluded that there were notable benefits in terms of reducing palpitations and vasovagal syncope over the course of eighteen months for eighteen patients; two patients discontinued due to lack of benefit.

Moreover, Barzilai et al performed an open-label trial without a placebo group in which they concluded that a single dose of 7.5mg Ivabradine significantly lowered the heart rate of POTS patients without any adverse side-effects. They also noted that Ivabradine maintained the sympathovagal balance despite the significant difference in heart rates between baseline and treatment; they postulate the dosing may be a contributing factor.

Furthermore, many of these prior studies strongly recommend the need for a randomized double-blind placebo-controlled clinical trial in order to measure the efficacy and effectiveness of only prescribing Ivabradine to patients with POTS. Thus, based on prior studies, the goal of this proposal is to evaluate a potentially effective treatment method for POTS with Ivabradine.

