## **9. RESEARCH DESIGN AND METHODS**

**Overall Study Design.** The clinical trial will be registered under [www.clinicaltrials.gov](http://www.clinicaltrials.gov). Subjects between the ages of 18-65 who have a POTS diagnosis will be enrolled. Specifically, we will enroll patients who have hyperadrenergic POTS as confirmed by norepinephrine (NE) levels > 600 pg/ml. This is a 3-month study with a randomized double-blind placebo controlled cross over design. Subjects will be randomized into one of two groups (Ivabradine or placebo for one-month) then crossed over after a one-week washout period to the other group for one-month. Refer to Figure 1 below for details.

[figure not shown]

Figure 1. Randomized double-blind placebo-parallel group crossover trial with Ivabradine for patients with POTS.

**Study Visits.** There will be seven visits at the ACTRI and UCSD Cardiology clinics.

-Visit 1 is the pre-screening visit during which norepinephrine (NE) blood results will be obtained to confirm hyperadrenergic POTS diagnosis (NE> 600pg/ml). Orthostatic heart rate will be monitored. A urine pregnancy test will also be administered at this time. Post-menopausal women and women who are infertile will not be asked to take pregnancy test per PI discretion.

-At Visit 2, baseline lab work will be obtained to assess cardiometabolic health (CBC, CMP, TSH, T4, BNP). A tilt table test will be performed to determine baseline heart rate and QOL questionnaire (ShortForm36, SF36) will be completed. Orthostatic heart rate will be monitored. At this point, the patient will be randomized into the Ivabradine or placebo group for one month.

-At Visit 3, two-weeks into treatment, the patient will return to ACTRI for drug titration. Orthostatic heart rate will be monitored. If the patient fulfills criteria (see **Ivabradine Dosing** below), they will either increase, decrease, stop, or not change their Ivabradine dose.

-At Visit 4, one month after starting the current treatment, orthostatic heart rate monitoring, NE bloodwork, and QOL questionnaires will be completed. There will be a one-week wash-out period before the patient crosses over to the other group for one month.

-At Visit 5, the patient will return for orthostatic heart rate monitoring, NE bloodwork, and QOL questionnaires. A urine pregnancy test will be administered at this time. Post-menopausal women and women

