who are infertile will not be asked to take pregnancy test per PI discretion. The patient will be instructed to begin the secondary treatment (placebo or Ivabradine) for one month.

-At Visit 6, two-weeks into this treatment, the patient will return to ACTRI for drug titration. Orthostatic heart rate will be monitored. If the patient fulfills criteria (see **Ivabradine Dosing** below), they will either increase, decrease, stop, or not change their Ivabradine dose.

-At Visit 7, one month after starting the secondary treatment, the patient will return for orthostatic heart rate monitoring, NE bloodwork, and QOL questionnaires.

Blood samples will be saved and securely stored with the PI for future research analysis and purposes.

**Randomization.** Randomization refers to the order in which patients receive placebo or Ivabradine. If a patient receives Ivabradine first for one month, then he/she will be switched over to placebo for one month. If a patient receives placebo first for one month, then he/she will be switched over to Ivabradine for one month. There will be a one-week washout period prior to the cross-over. There will be 10 patients in each group.

**Ivabradine Dosing.** Ivabradine dose will initiate at 5mg twice daily (bid) and be increased to 7.5mg twice daily (bid) after 2 weeks if the heart rate is greater than 70 beats/min. If the heart rate is less than 70 beats/min there will no increase in dose. If the heart rate is less than 50 beats/min, or if the patient has symptoms of dizziness or lightheadedness, then Ivabradine will be stopped.

If patients have side effects and feel that cannot continue with Ivabradine we will decrease the dose from 7.5mg bid to 5mg bid (or if they are on 5mg bid to 2.5mg bid). After this dose reduction if the patient is still unable to tolerate Ivabradine, we will stop Ivabradine and withdraw patient from the study. If a patient is unable to tolerate Ivabradine (particularly prior to crossover period), he/she will be withdrawn. The starting dose and titration model is the same for the crossover treatment period as the initial month.

In our clinical experience using Ivabradine in patients with inappropriate sinus tachycardia (which are very similar to POTS patients in age and co-morbidities) we have not seen significant side effects that have caused patients to stop the drug. Refer to the uploaded Ivabradine Drug Information document for more details.

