**Statistical Analysis.** Continuous variables including mean heart rate, maximum heart rate, and quality of life scores will be summarized using descriptive statistics, including the number of observation (n) mean, standard deviation (SD), standard error (SE), median, the 1st (Q1) and 3rd (Q3) quartiles, minimum, and maximum values. The change in heart rate at one month from baseline will be compared by T-tests based on treatment status with placebo versus Ivabradine. Categorical variables will be compared by McNemar's test based on treatment status with placebo versus Ivabradine.

The study design will be adaptive and data analysis will be done in batches. The PI and others involved in data analysis will be blinded to who is the Ivabradine group and who is in the placebo group.

**Power Analysis.** Assuming a decrease in average heart rate of 10 beats/min is clinically significant (e.g. Decrease from 100 to 90; magnitude of effect 10%) with power 0.8 and standard deviation in heart rate is 7.5 beats/min, the estimated sample size is 18 patients. We will enroll 10 patients in each group to account for the 10% drop-out rate and to ensure the study is adequately powered. For sample size calculation, two-sided alpha level = 0.05 and two sample t-test are used.

**Drop-outs.** If any patient decides to withdraw from the study due to the intolerance of side-effects, we will try to obtain a tilt table test, orthostatic heart rate, QOL questionnaire, and blood tests at the time of drop-out.

**Documentation.** All patient related documentation will be stored at UCSD for future analysis as funding becomes available. To minimize the potential loss of confidentiality, patients will be assigned a unique number as their subject identifier code. The unique subject code will be used to label all study documents. The key that relates the code numbers to the individuals will be kept in a locked cabinet in the PI's office at the ACTRI.

All procedures mentioned above are research procedures and are not part of standard care.

Results may be used for diagnosis, treatment, and prevention of disease in patients.

**Incidental findings that result from the conduct of this study that require medical intervention for the subject will be noted by the PI or her project's medical research staff. They will refer the subject to his primary care physician. If the subject does not have a primary care physician one will be appointed for him or her.**

---

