  - b. In the event of an AE that occurs during the appointment, the facility is equipped with trained medical staff (physicians and nurses) who can respond quickly. Should an event occur, [name] and the nurses will be nearby to administer immediate medical care and send the patient to the nearest hospital. If the AE occurs after the appointment, the patient will be referred for prompt medical attention. The patient will be withdrawn from the study. [name] will monitor the patient until the problem has been resolved or has stabilized.
3. Orthostatic heart rate monitoring:

- a. Prior to enrollment, the patient will be informed about the risks of orthostatic heart rate monitoring. The physician will comfort the patient to reduce anxiety/fear in order to minimize the probability of a vasovagal response. [name] will continuously monitor and oversee the procedure by checking vital signs. The patient may contact [name] for further questions/concerns.
  - b. In the event of an AE that occurs during the appointment, the facility is equipped with trained medical staff (physicians and nurses) who can respond quickly. Should an event occur, [name] and the nurses will be nearby to administer immediate medical care and send the patient to the nearest hospital. If the AE occurs after the appointment, the patient will be referred for prompt medical attention. The patient will be withdrawn from the study. [name] will monitor the patient until the problem has been resolved or has stabilized.
4. Consuming Ivabradine
- a. [name], a cardiologist, will give the patients specific instructions on the amount of ivabradine capsules they would need to consume each day. A research person will follow up with the patient the next day and once a week for the next 90 days to assess the patient's condition. The patient's conditions will be reported back to the PI. If the patients have reasons to believe that Ivabradine is causing any discomfort, consumption of the capsule will be stopped.

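### Dizziness or lightheadedness stops study drug without qualification, while other instructions increase, reduce or withdraw for the same patient, and the handling of mandated stops is not planned

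*Combined protocol and SAP*

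**What the plan says.** All references are to the combined protocol and SAP.

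- **Section 9, Study Visits.** The dosing criteria are applied at Visit 3, "two-weeks into treatment, the patient will return to ACTRI for drug titration", and again at Visit 6 in the second period. Section 9, Ivabradine Dosing, uses the same starting dose and titration scheme in both periods.
- **Section 9, Ivabradine Dosing, first paragraph.** The dose goes up after two weeks "if the heart rate is greater than 70 beats/min" and does not go up below 70. The stop sentence then names a heart rate below 50, "or if the patient has symptoms of dizziness or lightheadedness, then Ivabradine will be stopped".
- **Same heading, second paragraph.** For patients with side effects who feel unable to continue, "we will decrease the dose from 7.5mg bid to 5mg bid", or from 5 mg to 2.5 mg. Only if the lower dose is not tolerated is drug stopped and the patient withdrawn.
- **Section 15, AE Management, item on consuming ivabradine.** "If the patients have reasons to believe that Ivabradine is causing any discomfort, consumption of the capsule will be stopped". The text that follows withdraws patients who have an adverse event.
- **Section 9, Drop-outs.** For patients who choose to withdraw because of side effects, the team will try to obtain a tilt test, orthostatic heart rate, questionnaire and bloods at that time.
- **Section 9, Study Visits and Specific Protocols.** The scheduled measures are orthostatic heart rate, norepinephrine, SF-36 and a baseline tilt test. No dizziness or lightheadedness item is named at any visit.

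**The concern.** The word *or* frees the symptom part of the stop sentence from any heart-rate condition. It also carries no condition on severity, onset, cause or change since before dosing. The increase sentence has no symptom condition, and nothing says which sentence governs when both apply. Two assessors could act differently on the same patient and both be following the protocol.

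There is also a statistical consequence. If a stop can be triggered by a symptom the patient already had, stopping reflects the condition under study as well as drug effect, in placebo and ivabradine periods alike. A patient stopped at week 2 reaches the one-month heart-rate reading off treatment, or does not reach it. The first dilutes the primary comparison if the stop is on ivabradine; the second makes the analysed group selective. With 20 patients and a 10% drop-out allowance, there is little room for either.

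**Working it through.** **1. The instructions side by side.** Take a patient at week 2 with a heart rate of 95 who reports lightheadedness.

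| Instruction | Condition | Met? | Action |
|---|---|---|---|
| Dosing, para 1, increase | rate above 70 | yes | increase |
| Dosing, para 1, stop | rate below 50, or dizziness/lightheadedness | yes, by the symptom | stop |
| Dosing, para 2 | side effects, patient feels unable to continue | if the symptom is taken as such | reduce first |
| AE Management, discomfort | patient attributes it to drug | if so attributed | stop |
| AE Management, adverse event | symptom counted as an adverse event | if so counted | withdraw |

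The first two rows conflict on the text alone, at any rate above 70. The others may join, depending on how the symptom is classified. The first paragraph does not say whether a symptom stop ends participation or lets the patient continue to crossover.

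**2. The plan's sample size.** Inputs from section 9, Power Analysis: difference 10 beats/min ("Decrease from 100 to 90; magnitude of effect 10" per cent), SD 7.5, two-sided alpha 0.05, power 0.8, two-sample t-test.

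- n per group = 2 × (1.960 + 0.842)² × 7.5² / 10² = 8.83, rounded up to 9, total 18. This reproduces the plan.
- 18 / 0.90 = 20, the planned enrolment.
- Noncentral t power: 75.7% with 9 per group, 80.5% with 10 per group.

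**3. Illustration: stopped on ivabradine, still measured.** The documents give no stop rate, so a share s from 10% to 50% is assumed, with complete loss of drug effect after a stop. Patients who stay are counted, so 10 per group applies. The difference becomes 10 × (1 − s). The noncentrality is that difference divided by 7.5 × √(2/10) = 3.354, with 18 degrees of freedom.

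| s | Difference | Noncentrality | Power |
|---|---|---|---|
| 0% | 10 | 2.98 | 80.5% |
| 10% | 9 | 2.68 | 71.8% |
| 20% | 8 | 2.39 | 61.7% |
| 30% | 7 | 2.09 | 50.6% |
| 40% | 6 | 1.79 | 39.5% |
| 50% | 5 | 1.49 | 29.2% |

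**4. Illustration: stopped and lost.** If the same shares of all 20 patients left the analysis and the difference stayed at 10, power would be 75.7%, 69.9%, 63.0%, 55.0% and 45.8% for 10% to 50% lost. This shows the loss of numbers only, not any selection bias.

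**5. How often heart rate alone would stop drug.** Using normal tail areas, the plan's means of 100 or 90 with SD 7.5 put at least 99.6% of patients above 70 and fewer than 1 in 10 million below 50. Posture is not stated in the dosing rule, and section 10 excludes only resting rates below 60. An assumed resting mean of 75, less the plan's 10-beat effect, gives 65. With an assumed SD of 10, 31% are above 70 and 6.7% below 50. The answer depends on the assumed mean.

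**The case against.** **The sentences have a natural order.** A rate of 45 already meets both the no-increase and the stop sentences, and anyone would stop. Read the same way, a lightheaded patient at 95 is stopped. That is a fair reading of increase against stop. It does not settle stop against reduce-first, or whether a stop means withdrawal.

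**An unqualified symptom stop may be a deliberate safety choice.** It may be, and nothing here says it is the wrong rule. The point is that the text gives more than one instruction.

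**The disease link is not in the documents.** A reader might infer that lightheadedness is expected in untreated and placebo patients. The documents name tachycardia on standing, weakness, palpitations, tingling or coldness, and fatigue. For one series of twenty POTS patients they report "notable benefits in terms of reducing palpitations and vasovagal syncope over the course of eighteen months". They do not list lightheadedness as a POTS symptom, so only the weaker statement stands: the rule can be triggered by a symptom already present.

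**Symptoms are not wholly unrecorded.** Screening includes history and examination, SF-36 is completed at Visits 2 and 5, and adverse events are followed the next day and weekly. What stands is that no dedicated dizziness item is named before dosing in either period.

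**Stopped patients are partly covered.** The Drop-outs text seeks measurements at withdrawal. But it concerns patients who decide to leave for intolerance, not those the protocol stops, and it does not ask for the one-month reading.

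**The power figures use a parallel-group test in a crossover.** True. They follow the plan's own calculation. A paired analysis would give different values, and the documents give no within-patient correlation.

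**Conclusion.** The concern holds as a contradiction between instructions, plus a gap in how mandated stops are recorded and analysed. Both follow from the text and need no clinical assumption.

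Its numerical size is unknown. The fall from 80.5% to 72-29% power rests on an assumed 10-50% stop rate on ivabradine, complete loss of effect after a stop, all stopped patients measured, and the plan's two-sample test with 10 per group. It shows sensitivity and is not a forecast. Stopping placebo in a patient who is still measured removes no drug effect, so placebo stops do not enter that calculation; they matter if they lead to loss or unequal handling.

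Two stronger readings are not supported. A reader might infer that the symptom criterion decides nearly every stop. That follows at means of 90 to 100 but not at an assumed mean of 65 and SD of 10, where 6.7% fall below 50, and other stop routes also exist. A reader might also infer that a large share of placebo patients would be stopped; the documents give no symptom rate from which to say so.

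**What to change.** 1. The investigators should reconcile the increase, reduce, stop and withdraw instructions in section 9 (Ivabradine Dosing) and section 15 (AE Management). The text should state which takes precedence when several apply, whether symptoms present before dosing count, and whether a symptom stop means withdrawal or continuation to crossover. The clinical content is theirs to decide.
2. Record dizziness and lightheadedness at Visits 2 and 5 before dosing, and at Visits 3, 4, 6 and 7.
3. Report stops by reason (heart rate, symptom, other) and by treatment period.
4. For patients stopped but still in the study, take the Visit 4 or Visit 7 heart rate as scheduled and analyse it under the randomised treatment. Extend the Drop-outs text to cover protocol-mandated stops.

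The cost is some protocol wording and one more item on forms at existing visits. No extra visit or procedure is needed.

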### **Management of risks to subjects**

#### *Expected AEs*

1. Blood draw
  - a. Hematoma
  - b. Arterial puncture
  - c. Pain
  - d. Nerve damage
  - e. Re-bleeding
  - f. Allergy
  - g. Phlebitis
  - h. Vasovagal reaction
  - i. Anxiety/fear
2. Tilt table test
  - a. Prolonged hypotension
  - b. Increased tachycardia
3. Orthostatic heart rate monitoring
  - a. Acute hypotension
  - b. Increased tachycardia
4. Consuming Ivabradine
  - a. Bradycardia

- b. Hypertension
  - c. Atrial fibrillation
  - d. Luminous phenomena (phosphenes)
5. Washout period
- a. Increased risk for cardiovascular events such as tachycardia

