  - b. In the event of an AE that occurs during the appointment, the facility is equipped with trained medical staff (physicians and nurses) who can respond quickly. Should an event occur, [name] and the nurses will be nearby to administer immediate medical care and send the patient to the nearest hospital. If the AE occurs after the appointment, the patient will be referred for prompt medical attention. The patient will be withdrawn from the study. [name] will monitor the patient until the problem has been resolved or has stabilized.
5. Washout Period
- a. [name] will monitor the patients closely during this washout period. [name] will remove patients from the study if it is in their best medical interest. A research person will follow up with the patient once a week during this period to assess the patient's condition. The patient's conditions will be reported back to the PI.
  - b. If an AE occurs, the patient will be referred for prompt medical attention. The patient will be withdrawn from the study. [name] will monitor the patient until the problem has been resolved or has stabilized.

In the event that a patient either withdraws from the study or the investigator decides to discontinue a patient due to SAE, the patient will have appropriate follow-up medical monitoring. Monitoring will continue until the problem requiring hospitalization has resolved or stabilized with no further change expected, is clearly unrelated to study medication, or results in death.

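### Side effects on Ivabradine lead to dose reduction, stopping or study withdrawal depending on the section read, and withdrawal can cost the one-month heart rate for treatment-linked reasons

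*Combined protocol and SAP*

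**What the plan says.** Section 9, Ivabradine Dosing, sets out a stepwise rule: "If patients have side effects and feel that cannot continue with Ivabradine we will decrease the dose", from 7.5 to 5 mg or from 5 to 2.5 mg twice daily. Then: "After this dose reduction if the patient is still unable to tolerate Ivabradine, we will stop Ivabradine and withdraw patient from the study". The same section stops the drug outright for a heart rate below 50, or for dizziness or lightheadedness.

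Section 15, AE Management, has its own rules.
- Item 4a (Consuming Ivabradine): "If the patients have reasons to believe that Ivabradine is causing any discomfort, consumption of the capsule will be stopped". There is no reduction step.
- Item 4b: "If the AE occurs after the appointment, the patient will be referred for prompt medical attention. The patient will be withdrawn from the study". Items 1b to 3b close in the same way.
- Item 5b (Washout Period): "If an AE occurs, the patient will be referred for prompt medical attention. The patient will be withdrawn from the study".
- For serious events, the closing paragraph covers the case where "the investigator decides to discontinue a patient due to SAE".

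Section 15 defines an adverse event without regard to relatedness and includes mild events. Its list of expected events includes tachycardia with orthostatic testing and, for washout, "Increased risk for cardiovascular events such as tachycardia".

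The Drop-outs paragraph of Section 9 says staff will try to obtain tilt test, orthostatic heart rate, questionnaire and blood results at exit from patients who decide to leave because of side effects. It does not say whether those values are analysed.

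**The concern.** Three instructions compete for the same patient, and no text ranks them. A patient who is stepped down stays in the trial and supplies a one-month heart rate on a lower dose. A patient who is withdrawn may supply none. So the section that staff happen to follow can decide who contributes to the primary endpoint.

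The loss is not obviously random. Bradycardia is an expected effect of the drug, and tachycardia is both an expected event of testing and washout and the condition under study. Withdrawal can therefore depend on treatment and on heart rate itself. Tolerability would also be reported for patients handled under different rules.

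**Working it through.** **1. One patient, three rules.** Take a patient on 7.5 mg twice daily with phosphenes (a listed expected event) who feels unable to continue.

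| Source | Action | Stays in study? |
|---|---|---|
| Section 9, Ivabradine Dosing | Reduce to 5 mg; stop only if still intolerant | Yes, unless the reduction fails |
| Section 15, item 4a | Stop the capsule | Not stated |
| Section 15, item 4b | Withdraw after the event | No |

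Section 9 also has an internal overlap: dizziness is a side effect, which points to reduction, and a named stop criterion, which points to stopping.

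**2. What happens to the endpoint.** Section 9 ends persistent intolerance in study withdrawal, and items 1b to 5b of AE Management do the same after an event. The Drop-outs paragraph covers only patients who choose to leave for intolerance, so a patient withdrawn by the investigator is outside it. Neither group is asked to return for Visit 4 or Visit 7.

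**3. The plan's own sample size.** Inputs from Section 9, Power Analysis: difference 10 beats/min, SD 7.5, two-sided alpha 0.05, power 0.8, two-sample t-test. The normal approximation gives n per group = 2 × (1.960 + 0.842)² × 7.5² / 10² = 8.83, rounded up to 9, so 18 in total. Then 18 / 0.9 = 20. Both figures reproduce. The planned allowance is 2 losses.

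**4. Power after losses, counting patients as a crossover does.** Each completer gives one Ivabradine value and one placebo value. For m completers with between-period correlation ρ, the SD of the difference is 7.5 × √(2(1 − ρ)), and the paired t-test has noncentrality 10√m / SD and m − 1 degrees of freedom. With ρ = 0 the SD is 10.61; for m = 14 the noncentrality is 10 × 3.742 / 10.61 = 3.53 on 13 degrees of freedom, and power is 0.903.

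| Completers | Paired, ρ = 0 | Paired, ρ = 0.3 | Unpaired, m values per treatment |
|---|---|---|---|
| 18 | 0.964 | 0.994 | 0.973 |
| 16 | 0.941 | 0.988 | 0.954 |
| 14 | 0.903 | 0.973 | 0.924 |
| 12 | 0.844 | 0.944 | 0.877 |
| 10 | 0.756 | 0.886 | 0.805 |

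The correlations are assumed, and 7.5 is taken as the SD of a single measurement. Eleven completers are enough for 80% power even at ρ = 0.

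**5. Chance of exceeding the allowance.** For an assumed withdrawal probability p per patient, P(more than 2 of 20 lost) is 7.5%, 32%, 79% and 96% at p = 5%, 10%, 20% and 30%. At p = 30% the expected number left is 14, the 90% row above.

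**6. Bias, as an illustration only.** Assume on-drug rates are normal with SD 7.5. If the 2 lowest of 20 are lost, the on-drug mean rises by 1.4 beats/min (2.5 if the 4 lowest are lost). By symmetry, losing the 2 highest lowers it by 1.4. If each lost patient's placebo value goes too, the shift in the treatment difference is 1.4 × (1 − ρ), or 0.7 at an assumed ρ = 0.5. If losses are unrelated to heart rate, the shift is 0. The documents do not show which pattern applies.

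**The case against.** Several points against this carry weight.

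- **The withdrawal sentence may be narrower than it looks.** In items 1b to 4b it follows references to immediate care, hospital or prompt medical attention, and Section 15 defines a mild event as one needing no special treatment. A reader might infer that every adverse event forces withdrawal, or that mild events are treated more strictly than serious ones. The documents do not establish either. Item 5a also leaves removal during washout to the patient's best medical interest. But the limit is never stated, and item 5b is conditioned only on an event occurring.
- **Item 4a and Section 9 could run in sequence.** Item 4a stops the capsule and reports to the PI; it does not say withdraw. A pause followed by a step-down is possible, but the text does not say that the stop is temporary.
- **A reader might infer that a third loss leaves the trial underpowered.** That treats the remaining patients as two parallel arms. The power paragraph does use a two-sample formula, but every patient is crossed over, and the power margin is wide (working, step 4).
- **A reader might infer that the losses must shrink the effect.** They need not. Tachycardia during on-drug testing would remove poor responders and inflate it. The below-50 stop belongs to Section 9 and applies whichever rule is followed, so it does not arise from the conflict.
- **Tolerability may be good.** Section 9 reports no significant side effects leading to stopping in similar patients. Section 7 cites 20 patients of whom 2 discontinued, for lack of benefit.

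These points limit the size of the problem. They do not settle which instruction applies or recover the missing endpoint.

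**Conclusion.** The point holds as a conflict of instructions combined with avoidable loss of the primary endpoint. The clash between dose reduction in Section 9 and stopping in item 4a stands even on the mildest reading of the withdrawal sentences. The consequence is inconsistent handling and possible bias of unknown direction and size; the shifts in step 6 show scale under assumed selection and are not estimates. Power is not the issue: about 90% or more remains with 14 completers, given the plan's 10 beats/min and SD 7.5 per measurement and a between-period correlation of zero or above. How often the conflict would arise cannot be judged, because the documents give no adverse event or intolerance rate for this trial. The change is worth making because it is cheap and lowers the risk of bias.

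**What to change.** 1. **Section 15, item 4a.** Discomfort attributed to the capsule leads to the Section 9 dose-reduction steps. Stop at once only for a Section 9 stop criterion (rate below 50, dizziness or lightheadedness), investigator judgement or patient request.
2. **Section 15, items 1b to 5b.** Replace automatic study withdrawal with stopping study drug if the event is serious or the investigator judges it unsafe to continue. State that tachycardia typical of the patient's POTS, on standing or in washout, is not by itself a reason for withdrawal.
3. **Section 9, Ivabradine Dosing.** A patient who cannot tolerate the drug stops that period's treatment. Unless consent is withdrawn, the patient stays in follow-up, gives the planned Visit 4 or Visit 7 heart rate, and may enter the next period if safe.
4. **Section 9, Statistical Analysis and Drop-outs.** Analyse all available one-month heart rates by the treatment assigned for that period. Report reductions, stops and withdrawals by treatment and reason. Show an on-drug analysis as a sensitivity analysis.

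The cost is a few replaced or added sentences and no new visit type; patients who stop early would still attend visits already planned. The downside is that including patients who stopped dilutes the on-drug effect somewhat, which is why the sensitivity analysis is shown.
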